## **15. Withdrawal of Subjects**

If at any time a participant decides to withdraw from the study, the participant will be debriefed by the study coordinator or principal investigator as to the reason for their withdrawal. The participant will then be thanked for their time and compensated for the extent of their participation. If the participant wishes to withdraw, they will be asked if they will allow data already collected on them to be used in the study analysis. If not, the data associated to their identifying code will be purged from the study database. A participant could be excluded and withdrawn from the research study in the event that a pre-determined condition exists, including a defined neurological or neurodegenerative disorder (e.g., traumatic brain injury, epilepsy, Alzheimer's disease), other psychiatric conditions (e.g., schizophrenia, bipolar disorder), current drug or alcohol use disorder (except for nicotine), and/or contraindications to MRI.

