## **14. Provisions to Monitor the Data to Ensure the Safety of Subjects**

Data safety and monitoring will be carried out to ensure and maintain the scientific integrity of this project and to protect the safety of our participants. Safety monitoring is the process during the study that involves review of accumulated outcome data for groups of subjects to determine if any of the procedures practiced should be altered or stopped. Ultimately, the PI ([name]) will be responsible for monitoring the safety of the study and complying with the reporting requirements. An independent Data Safety and Monitoring Board (DSMB) will review the study data on a biennial basis with the PI to ensure participant safety (re: subject recruitment at 20 subjects/year, DSMB meetings every ~ 10 participants). The Data Safety and Monitoring Board will include [name] [name] (DSMB Chair/Dept. of Neurology), [name] (Dept. of Anesthesiology), and [name] (PI at Mind Research Network). The board members have no conflicts of interest or roles with the current project. Drs. [name] and [name] have experience participating in ECT-related DSMB, and [name] has extensive clinical experience with ECT. Continuous, close monitoring of participant safety will include prompt and frequent reporting of safety data (i.e., adverse/serious adverse events) to the DMSB, the University of New Mexico Health Sciences Center Institutional Review Board (UNMHSC IRB) and/or appropriate NIH staff with oversight responsibility. The focus of adverse event reporting will be the first treatment of the ECT series, which is the only experimental treatment for this phase of the project. The first treatment will be amplitude titration (as opposed to the more traditional titration based on pulse number or frequency). The amplitude titration will result in reduced amplitudes (hypothesized range will be between 250 and 550mA, traditional ECT is conducted at 800mA). Adverse events may include expected side effects related to ECT: headaches, nausea (from anesthesia), and muscle aches (from anesthesia). Unexpected side effects (to be determined) will also be reviewed with the DSMB. In addition, relevant published data related to the study protocol will also be presented to the DSMB. The DSMB will evaluate the adverse effects of the first treatment in relation to the expected side effects related to a traditional ECT series. The PI will provide a summary of the safe conduct of the study to NIH and FDA on an annual basis as part of the progress report. All AEs occurring during the course of the study will be collected, documented, and reported to the UNMHSC IRB. The review of data may result in early termination of the study, amendment to the protocol, or changes to

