*The risks of low-amplitude seizure and motor titration will be minimal relative to the traditional (higher) ECT amplitudes. The experimental portion of this protocol is relevant only to the first treatment with the remaining treatments completed at the traditional 800 mA amplitudes. Subjects will also receive more comprehensive clinical and neuropsychological assessments by participating in this research protocol relative to routine clinical care.*

7. If this study involves a health or behavioral intervention, describe why the relation of the anticipated benefit to the risk of the research is at least as favorable to the subjects as that presented by alternative procedures.

*This investigation proposes use amplitude titration relative to the traditional pulse-number based titration and fixed amplitude ECT. This difference is only relevant to the first treatment. The remaining treatments will be completed with traditional 800 mA ECT.*

8. Describe your plans for monitoring the well-being of subjects including any plans to withdraw subjects from the research if they appear to be unduly distressed.

*Subjects that appear to be distressed will be encouraged to withdraw from the study protocol. If subjects appear to be unduly distressed, the study PI will withdraw these subjects from the protocol. Data regarding subject drop-out will be documented and presented to the DSMB.*

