## 47. Data Transfer/Sharing (Checklist)

Complete this checklist if the research involves transferring/sharing of data with an external entity (institution, company, etc.).

A. Will data be transferred/shared with an external entity (institution, company, etc.)?

Yes

No. **The remainder of this section does not apply.**

B. Indicate if the data is incoming and/or outgoing: Outgoing

C. Provide the name of the entity that data will be transferred/shared with: De-identified clinical and imaging data will be uploaded to the National Institute of Health National Data Archive at 6-month intervals. This is an NIH requirement.

D. Provide the contact name, email and phone number with whom data is being transferred or shared with: <https://nda.nih.gov>

E. Who is responsible for transmission of the data? Study PI ([name]) and team

F. Who is responsible for receiving the data? NIMH Data Archive

G. Describe how the data will be transferred/shared. Please note data cannot be transferred/shared without assistance from UNM HSC IT. **Requesting HSC Central IT Transfer is detailed on the Sponsored Projects website:** De-identified data will be uploaded to NIMH Data Archive through the COINS (<https://coins.trendscenter.org>) system.

H. For data being transferred/shared with outside locations or entities, describe the following:

- Where is data storage and how will it be maintained in a secure manner (i.e. encryption, password protection, use of Qualtrics or REDCap, etc)? <https://coins.trendscenter.org>. Data is encrypted and password protected.
- What is method in which data will be collected and stored (i.e. electronic, hard copy, etc)? Data will be initially recorded in paper charts and then electronically uploaded to COINS site. The data will be then be uploaded at 6-month intervals from COINS to the NIMH Data Archive.
- How long will the data be stored? *Paper charts will be kept for the duration of the study. COINS and NIMH Data Archive (de-identified data) will be kept indefinitely.*
- Who will have access to data? *Study team will have access to the COINS data; Other investigators must access NIMH Data Archive through established protocols (<https://nda.nih.gov/get/access-data.html>).*

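### Section 15 purges a withdrawing subject's data on refusal of analysis use, with no exception for adverse events or disposition, which undercuts the cumulative safety review in Sections 14 and 44.A

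*Protocol*

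**What the plan says.** Protocol Section 15 covers a participant who decides to withdraw. After a debriefing about the reason, "they will be asked if they will allow data already collected on them to be used in the study analysis". The consequence of a refusal follows directly: "If not, the data associated to their identifying code will be purged from the study database". No class of data is excepted, there or elsewhere in the protocol or SAP.

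Three other statements depend on the same data:

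- Section 14 on adverse events: "All AEs occurring during the course of the study will be collected, documented, and reported to the UNMHSC IRB".
- Section 14 on monitoring, which it describes as "review of accumulated outcome data for groups of subjects to determine if any of the procedures practiced should be altered or stopped". The schedule is "DSMB meetings every ~ 10 participants", and the board is to judge the adverse effects of the first treatment against those expected of a traditional ECT series.
- Section 44, part A, item 8, on subjects who leave: "Data regarding subject drop-out will be documented and presented to the DSMB". The same item says that subjects who appear distressed will be encouraged to withdraw, and that the investigator will withdraw those who are unduly distressed.

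**The concern.** The question put to the subject and the consequence of the answer do not match. The subject is asked about use in the analysis, but a refusal deletes everything under the code. Someone who only wants to stay out of the research results, and never asks for erasure, still loses their adverse event entries, first-treatment record and reason for leaving from the study database.

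This matters because of what the board is reviewing. Section 13 says that amplitude titration has not yet been done in humans with modern ECT parameters, Section 33 describes the device as investigational, and Section 14 makes the first treatment the focus of adverse event reporting. Section 14 also lets the review lead to early termination or amendment. With 40 subjects, a single record can change what a cumulative table shows. A purge takes the subject out of both the numerator and the denominator, and the protocol itself links distress to withdrawal.

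**Working it through.** **1. The rules side by side.**

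| Place | What must happen | Effect of a purge |
|---|---|---|
| Section 15 | On refusal of analysis use, all data under the code leave the study database | none: this is the purge itself |
| Section 14, adverse events | All are collected, documented and reported to the IRB | Reports already sent survive; the database entry does not |
| Section 14, DSMB | Accumulated data are reviewed about every 10 participants | Later cumulative counts lack the subject, as case and as exposed subject |
| Section 44.A item 8 | Drop-out data are documented and presented to the DSMB | The reason and disposition may be gone before the next presentation |

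A site can report an event and purge the entry afterwards, so there is no literal contradiction. What fails is the accumulated dataset with its denominators.

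**2. The plan's own attrition figure.** Section 6 gives 40 subjects and 20% attrition: 40 × (1 − 0.20) = 32, as stated. That is 8 subjects lost. Eight is the ceiling on purged records only if attrition is as planned, every loss is the subject's own withdrawal, and every one of them refuses. The documents support none of these assumptions specifically.

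**3. One purged record (illustration).** Suppose one subject of 40 has a non-serious adverse event, withdraws and declines analysis use.

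- Before the purge: 1/40 = 2.5%. The exact (Clopper-Pearson) 95% interval is 0.1% to 13.2%; the lower limit is 1 − 0.975^(1/40) = 0.06%.
- After the purge: 0/39 = 0%. The upper limit is 1 − 0.025^(1/39) = 9.0%.

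**4. Selective against non-selective loss (illustration).** Assume that 4 of 40 subjects (10%) have an event and 4 subjects are purged.

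| Purged subjects with the event | Rate left in the database |
|---|---|
| 0 | 4/36 = 11.1% |
| 1 | 3/36 = 8.3% |
| 2 | 2/36 = 5.6% |
| 3 | 1/36 = 2.8% |
| 4 | 0/36 = 0% |

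The direction depends on who refuses. If refusals are unrelated to events, the rate is roughly preserved. If they follow events, it falls toward zero.

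**5. Loss of information when refusal is unrelated to events.** The chance of at least one event in the database is 1 − (1 − p)^n. Going from n = 40 to the extreme n = 32:

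| Assumed event rate p | n = 40 | n = 32 |
|---|---|---|
| 1% | 33.1% | 27.5% |
| 2% | 55.4% | 47.6% |
| 5% | 87.1% | 80.6% |
| 10% | 98.5% | 96.6% |

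Even at that extreme the fall is modest. The problem is selective loss more than lost sample size.

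**The case against.** The strongest reply is that the purge is narrow and safety reporting is fast. Much of this stands.

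- **Timing.** Section 14 promises that "Continuous, close monitoring of participant safety will include prompt and frequent reporting of safety data (i.e., adverse/serious adverse events) to the DMSB", and to the IRB and/or NIH staff. An event will normally be reported before any purge, and a purge does not recall a report. However, separate reports are not a cumulative table with a denominator.
- **Scope.** Section 15 names only the study database. It does not name the case report forms in Section 16, or the paper charts that Section 47 keeps for the duration of the study. So the records are not all destroyed. Yet nothing tells the site to build safety summaries from those sources for a purged subject.
- **Trigger.** The subject must both withdraw and refuse. Withdrawal by the investigator under Section 44.A item 8 does not trigger the question in the text and is no evidence of selective loss.
- **Subject choice.** Honouring a refusal for research use is a legitimate decision. It gives no reason to override the subject's wishes on imaging or cognitive data.

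A reader might infer several stronger points that the documents do not support:

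- *Sections 14 and 44.A promise that these data are retained, so a site cannot obey both rules.* Those sections speak of collecting, documenting, reporting and presenting. None mentions retention.
- *A serious first-treatment event could vanish.* Section 14 says that significant events directly related to that treatment, such as hospitalization and death, will warrant suspension or termination. Such an event would normally have been reported and acted on already. The illustration is therefore confined to non-serious events.
- *The subjects who were harmed are the ones who will be deleted.* The documents link distress to withdrawal, but nothing links harm to refusal of data use.
- *The study database and the national archive will disagree.* Section 47 does say "De-identified clinical and imaging data will be uploaded to the National Institute of Health National Data Archive at 6-month intervals", but Section 17 refers to the consent form's data-sharing section, which is not among the documents available here. How withdrawal affects uploaded data cannot be judged.

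**Conclusion.** The point holds as a conflict in effect. Section 15 states a rule without a safety exception, and following it as written can remove adverse event, first-treatment and disposition data from the accumulated review that Sections 14 and 44.A rely on. It should be corrected.

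The size is unknown because no refusal rate is given. The change from 1/40 to 0/39 shows only how sensitive a 40-subject safety table is to one record. The possibility of selective loss rests on the encouragement of distressed subjects to withdraw, plus the assumption that some of them would then decline analysis use. No significance level, power figure or sample size in the plan is affected.

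**What to change.** Replace the purge sentence in Section 15 with a rule that separates the two uses of the data. Suggested text: *If the participant declines, their imaging, clinical and cognitive outcome data will be excluded from the research analyses. Adverse events, first-treatment and device records, the reason for withdrawal and disposition will be kept under the study code. Every treated participant will be counted in the safety summaries given to the DSMB.*

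Add a cross-reference in Section 14 and in Section 44.A item 8, and put matching wording in the consent form so that subjects know before they enrol.

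The cost is one amended sentence, two cross-references and a consent change through the IRB. The downside is small: subjects lose the option to erase safety and disposition records already collected. They keep control over use of their data in the research analyses.

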## **16. Data Management/Confidentiality**

Every effort will be made to protect the confidentiality of participants' records. However, complete confidentiality of records cannot be guaranteed as records may be examined by authorized personnel from the UNM Human Research and Review Committee. Participants will be informed of this possibility prior to signing the consent forms. Otherwise, records will be kept strictly confidential and will not be inspected by any other agency unless required by law. Behavioral and computerized data from the MRI scanning sessions will not contain participants' names or any other identifying information per HIPAA requirements. Data will be de-identified as appropriate to the UNM Human Research and Review Committee and HIPPA requirements by assigning a randomized eight-digit number to each participant upon entry into the study. This number will be used for all correspondence between study investigators and all data collection and analysis after the initial screening visit. MRN has a state-of-the art IT network with all necessary security mechanisms in place. Any personal information entered into computers is password protected and monitored for suspicious activity. In order to contact subjects for telephone visits and/or other matters, it will be necessary to retain names and telephone numbers of active subjects. However, these direct identifiers will not be stored with any clinical data or subject information in order to protect confidentiality. Any direct identifiers will be stored in locked cabinets, on a secure MRN server, and/or the COINS database on a secure HIPAA compliant cloud based server, separate from any clinical data. These will only be accessible by key study personnel. A link between study code numbers and direct

identifiers will be retained in order to contact subjects for visit appointments or at a later date to inform them of newly received information. This link will be retained for the duration of the study. Subjects will be identified only by unique Patient ID numbers in Case Report Forms (CRFs) and electronic CRFs. The CRFs will be maintained in a locked cabinet housed in the Center for Psychiatric Research. These documents will only be accessible by authorized study staff and will comply with HIPPA requirements for the storage of health information. Moreover, all information will be in double-locked rooms per HIPAA specifications. At the time of study closure, all participant identifiers (name, address, etc.) will be made inaccessible to the research team. MRN retains the link between identifiers and URSI indefinitely for the potential future benefit to the research participant. Specifically, it may become medically advantageous in the future for a former participant to have access to the clinical information that may be present in radiological scans and reviews. The results of this research may be presented at meetings or in publications; however, participants' identity will not be disclosed. The participant will be provided with a copy of the consent form to take home.

## **17. Data and Specimen Banking**

Data will be stored in locked cabinets at the UNM Center for Psychiatric Research. Subjects' charts will be stored without direct identifiers. Only research staff designated by [name] will have access to these records. Other than the research team, the study sponsor and the HRRC will be permitted access to the records. In order to contact subjects for telephone visits and/or other matters, it will be necessary to retain names and telephone numbers of active subjects. However, these direct identifiers will not be stored with any clinical data or subject information in order to protect confidentiality. Any direct identifiers will be stored in locked cabinets and on a secure MRN server, and/or the COINS database on a secure HIPAA compliant cloud based server, separate from any clinical data. These will only be accessible by key study personnel. A link between study code numbers and direct identifiers will be retained in order to contact subjects for visit appointments or at a later date to inform them of newly received information. Information collected will be labeled with a study number and will be entered in to a secure MRN server, and/or the COINS database on a secure HIPAA compliant cloud-based server. Data linking scan to identity will be maintained at the Mind Research Network indefinitely allowing the neuroradiologist to compare future scans with previous ones. Research data (not including scan data) will be de-identified after the study is complete and closure documents are submitted to the UNM IRB.

Electronic Data: Collaborative Neuroinformatics Suite (COINS). This cloud-based neuroimaging and neuropsychology software suite offers versatile, automatable data upload/import/entry options, rapid and secure sharing of data among PIs, querying and export all data, real-time reporting, and HIPAA and IRB compliant study-management tools suitable to large institutions as well as smaller scale neuroscience and neuropsychology researchers. Network is accessed on a secure MRN server, and/or a HIPAA compliant cloud-based server which has firewalls in place. Controlled access is granted to only study team members.

As per NIMH mandate, the de-identified data will be submitted to the National Institute of Mental Health Data Archive (NDA). NDA is a data repository run by the National Institute of Mental Health (NIMH) that allows researchers studying mental illness to collect and share de-identified information with each other. During and after the study, the UNM research team will send de-identified information to NDA. Other researchers nationwide can then file an application with the NIMH to obtain access to de-identified study data for research purposes. Experts at the NIMH who know how to protect health and science information will look at every request carefully to minimize risks to your privacy. In addition, de-identified information will be available at the Mind Research Network Data Sharing Repository for future research. Both the NDA and Mind Research Network Data Repositories are clearly described in the “Data Sharing” section of the consent form.

## **18. Risks to Subjects**

Participation in this study may involve minor risks and/or discomforts associated with possible breach of confidentiality risk, neuropsychological testing, MRI, and lower amplitude ECT.

Due to the coronavirus public health crisis, participants will receive regular COVID-19 testing as part of their standard ECT treatment procedure. Participation in this study may entail increase risk of exposure to COVID-19 during interactions with research staff. However, research staff adhere to all safety operating procedures required by UNM HSC, NMDOH and the CDC.

**MRI:** Radio and magnetic waves associated with MRI scans are not associated with any known adverse effects. MRI is non-invasive, non-contrast, and considered minimal risk by the FDA and OHRP. However, the scanner is a large magnet, so it could move objects containing ferrous metal in the room during the scan. All participants are screened using the MRI safety screening form prior to being scanned. Participants with any MRI scanning contraindications will be excluded from study participation. Participants may be bothered by feelings of claustrophobia (uncommon). The MRI also makes loud ‘drum’ beating noises during the study. Headphones are provided for protection. Rarely, large or recent tattoos can heat up during an MRI scan and cause skin irritation like a sunburn (uncommon). No long-term harmful effects from MRI are known. However, since the effect of MRI on early development of the fetus is unknown, participants who are pregnant will not be allowed to go in the MRI. Females 18 years of age or older who suspect they may be pregnant will be asked to take a urine pregnancy test before being allowed to participate in the study. The test results will only be shared with participant. The MRI risks include identification of incidental findings and potential cost for follow-up or clinical scans.

**Neuropsychological tests and clinical assessments:** The neuropsychological tasks involved in the protocol entail no foreseeable risk, besides perhaps fatigue or mild to moderate demands on attention and cognition.

